## **7.8. Serious Adverse Event Reporting**

An assessment of the seriousness of each AE will be made by the Investigator. Any AE and laboratory abnormality that meets the seriousness criteria above (Section 7.2) must be reported to Alnylam, or designee, within 24 hours from the time that site personnel first learn of the event, using the Serious Adverse Event Report provided. All SAEs must be reported regardless of the relationship to study drug. The SAE must also be recorded on the standard CRF pages.

The initial report should include at least the following information:

- Patient's study number,
- Description and date of onset of the event,
- Criterion for serious, and
- Preliminary assignment of causality to study drug.

In the first instance, AE reporting will be via electronic data capture (EDC). For names, addresses, telephone, and fax numbers for SAE reporting (eg, in case the EDC system is down), see information included in the SAE Reporting Procedure.

If follow up is required, new information should be provided to Alnylam, or designee, as it becomes available using the Serious Adverse Event Report. Copies of discharge summaries, consultant reports, autopsy reports, and any other relevant documents may also be requested.

Appropriate remedial measures should be taken by the Investigator or Sub-investigator using his/her best medical judgment to treat the SAE. These measures and the patient's response to these measures should be recorded. All SAEs, regardless of relationship to study drug, will be followed by the Investigator or Sub-investigator until satisfactory resolution or the Investigator or Sub-investigator deems the SAE to be chronic or stable. Clinical, laboratory, and diagnostic measures should be employed by the Investigator or Sub-investigator as needed to adequately determine the etiology of the event.

The Investigator will be responsible for reporting all SAEs to the IEC/Institutional Review Board (IRB). Alnylam, or designee, will be responsible for reporting of all relevant events to the regulatory authorities according to all applicable regulations.

In Europe, in accordance with the Directive 2001/20/EC, the Competent Authorities and the Ethics Committees in the concerned Member States will be notified of fatal and life-threatening Suspected Unexpected Serious Adverse Reactions (SUSARs) as soon as possible but no later than 7 calendar days after Alnylam or its representative has first knowledge of the minimum criteria for expedited reporting. Non-fatal and non-life-threatening SUSARs should be reported no later than 15 calendar days after Alnylam or its representative has first knowledge of them.

The Investigator may be informed by Alnylam or its representatives of SAEs from other Investigators or clinical studies that may have relevance to this clinical trial. These SAEs should also be reported promptly to the IEC/IRB that approved this study. All SAE reports should be transmitted to the IEC/IRB with a cover letter or transmittal form, and a copy of that transmittal should be maintained in the Investigator's files and forwarded to Alnylam as part of the trial master file on study completion.

## **7.9. Contraceptive Requirements**

### **7.9.1. Requirements for Women of Child-bearing Potential**

Women of child-bearing potential may be included in this study and include any female who has experienced menarche and who is not postmenopausal or permanently sterilized (eg, tubal occlusion, hysterectomy, or bilateral salpingectomy).

Women of child-bearing potential must have a negative pregnancy test and must be using 1 highly effective method of contraception in combination with a barrier method from the signing of the informed consent form (ICF), throughout study participation, and for 1 month after the last dose of ALN-TTRSC. Highly effective methods of birth control result in a low failure rate (ie, less than 1% per year).

For the purpose of this study, one of the following combinations of contraceptive methods must be used by WOCBP:

- Hormonal: established use of oral (except low-dose gestagens [eg, lynestrenol and norethisterone]), implantable, injectable, or transdermal methods of conception in conjunction with spermicide, condom, or diaphragm;
- Placement of an intrauterine device in conjunction with spermicide or condom;
- Placement of an intrauterine system in conjunction with spermicide or condom;
- Bilateral tubal occlusion in conjunction with spermicide or condom;
- Surgical sterilization of male partner (with the appropriate post-vasectomy documentation of the absence of sperm in the ejaculate; for female patients on the study, the vasectomized male partner should be the sole partner for that patient) in conjunction with spermicide, condom, or diaphragm;

- Sexual true abstinence: when this is in line with the preferred and usual lifestyle of the patient. Periodic abstinence (eg, calendar, ovulation, symptothermal, post-ovulation methods) and withdrawal are not acceptable methods of contraception.

Interaction between ALN-TTRSC and hormonal contraceptives is not anticipated; there were no effects of ALN-TTRSC on the reproductive organs (including histopathology) in any of the animal (rat and NHP) studies conducted to date. Moreover, ALN-TTRSC showed no inhibition in vitro of cytochrome P450 (CYP)1A2, CYP2C9, CYP2C19, CYP2D6 and CYP3A4/5 (both testosterone and midazolam were used as substrates in human liver microsomes).

#### **7.9.2. Requirements for Male Patients**

Males who agree to use appropriate means of contraception throughout study participation until 1 month after the last dose of ALN-TTRSC may be included in this study (see Section 7.9.1).

It is unknown if ALN-TTRSC poses any potential risk of drug exposure through the ejaculate. Male patients (including men who have had vasectomies), particularly those with partners who are pregnant, should use condoms (accompanied with spermicidal foam, gel, film, cream, or suppository) as the appropriate means of contraception for the duration of the study and until 1 month after study drug administration.

Males should also abstain from sperm donation after the first dose of study drug through study participation and for 1 month after the last dose of ALN-TTRSC.

#### **7.10. Pregnancy Reporting**

A female patient with a positive pregnancy test at Screening/Baseline is ineligible for this study. If a female patient becomes pregnant during this study, the patient must be instructed to stop all study drug administration. The Investigator or Sub-investigator must report a patient pregnancy (or a pregnancy of the partner of a patient participating in the study if consent has been obtained from the partner) to Alnylam or its agency within 24 hours of being notified of the pregnancy. Details of the pregnancy will be reported on a pregnancy report form. The patient/partner shall receive any necessary counseling regarding the risks of continuing the pregnancy and the possible effects on the fetus.

Monitoring of the patient/partner by the Investigator will continue until the conclusion of the pregnancy, and the Investigator will document the outcome of the pregnancy, which will be reported to Alnylam. If the outcome of the pregnancy meets the criteria for an SAE (ie, postpartum complication, spontaneous abortion, stillbirth, neonatal death, or congenital anomaly), then the Investigator should follow the procedures for reporting an SAE outlined above.

## 8. STATISTICAL METHODS

### 8.1. Sample Size

Approximately 25 patients who completed Study ALN-TTRSC-002 will be enrolled in this extension study.

### 8.2. Statistical Methodology

Statistical analyses will be primarily descriptive in nature. Adverse event summaries will include tabulations of all TEAEs, treatment-related AEs, SAEs, discontinuations due to AEs, and AEs of various grading severity.

Descriptive statistics will be provided for clinical laboratory data, vital signs data, and ECG interval data, presented as both actual values and changes from baseline relative to each on-study evaluation.

For categorical variables, summary tabulations of the number and percentage of patients within each category (with a category for missing data) will be presented. For continuous variables, the number of patients, mean, median, standard deviation, minimum, and maximum values will be presented.

A full statistical analysis plan will be finalized prior to database lock.

#### 8.2.1. Populations to be Analyzed

The following populations (ie, analysis sets) will be identified:

- Safety Analysis Set: All patients who receive at least one dose of ALN-TTRSC will be included in the safety analysis.
- PD Analysis Set: All patients who received at least one dose of ALN-TTRSC and have at least one blood sample post-dose assessment.
- PK Analysis Set: All patients who receive at least one dose of ALN-TTRSC and have at least one blood draw postdose to determine plasma concentrations of ALN-TTRSC will be included in PK analyses.

#### 8.2.2. Baseline Evaluations

Demographic and baseline disease characteristic data will be summarized. Data to be tabulated will include sex, age, and race, as well as disease-specific information.

#### 8.2.3. Safety Analyses

Adverse events will be summarized by MedDRA® system organ class and preferred term. Separate tabulations will be produced for all TEAEs, treatment-related AEs (those considered by the Investigator as at least possibly drug related), SAEs, discontinuations due to AEs, and AEs of various grading severity.

Descriptive statistics will be provided for clinical laboratory data and vital signs data, presented as both actual values and changes from baseline relative to each on-study evaluation and to the last evaluation on study.

Descriptive statistics will be provided for ECG interval data and presented as both actual values and changes from baseline relative to each on-study evaluation and to the last evaluation on study. Details of any abnormalities will be included in patient listings.

Details of any abnormalities will be included in patient listings.

#### **8.2.4. Clinical Activity Assessments**

Change from baseline by time point for 6-MWT will be summarized, where change from baseline is predose value (or final assessment from ALN-TTRSC-002, if a pre-dose assessment in this study is not required). Change from baseline will also be summarized where baseline is derived from predose assessments in ALN-TTRSC-002.

Frequency of hospitalization, cardiovascular hospitalization, and heart failure hospitalization will be summarized. All-cause mortality and cardiovascular mortality will be summarized using Kaplan-Meier curves.

Descriptive statistics will be presented for all clinical activity variables (NT-proBNP, troponin I, troponin T concentrations; selected echocardiography parameters; mBMI; NYHA classification; CMR imaging parameters). Patient reported QoL and disease burden will be assessed by summary statistics for the EQ-5D and KCCQ. Summary statistics will be provided for observed values and changes from baseline.

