Safety Assessments	
The safety of ALN-TTRSC will be evaluated by:
 
 
• Assessment of AEs
 
• Clinical laboratory safety tests (hematology and serum chemistry, including liver function tests, thyroid function, coagulation, and urinalysis)
 
• Vital sign measurements (blood pressure, pulse rate, oral body temperature, and respiratory rate)
 
• 12-Lead ECG
 
• Physical examinations
 
• Eye examinations
 

Pharmacodynamic Assessments	The PD effect of ALN-TTRSC will include assessment of serum TTR and vitamin A levels.
Pharmacokinetic Assessments	Blood samples for the assessment of ALN-TTRSC concentration and possible metabolite analysis will be collected predose and at various time points postdose.
Clinical Efficacy Assessments	
Clinical effects of ALN-TTRSC will be explored by:
 
 
• Mortality (cardiovascular-related and all-cause)
 
• Hospitalization (cardiovascular-related and heart-failure-related)
 
• 6-MWT
 
 
Additional exploratory clinical assessments include:
 
 
• Echocardiography
 
• Cardiac biomarkers (NT-proBNP, troponin T, and troponin I)
 
• KCCQ
 
• mBMI
 
• NYHA classification
 
• 99mTc imaging
 
• CMR imaging with gadolinium
 
• Fat pad aspirates for amyloid quantitation
 
• EQ-5D QoL
 
• Blood pressure
 
• eGFR
 
• New onset or recurrent atrial fibrillation
 
• Pacemaker placement
 
• Changes in diuretic regimen
 

Other Assessments	Other effects of ALN-TTRSC will be evaluated by: 

• Measurement of exploratory biomarkers and serology (ADAs)

• Determination of pharmacoeconomic outcomes through disease burden and healthcare utilization questionnaire.

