Familial amyloidotic cardiomyopathy is caused predominantly by the V122I mutation that is found in up to 4% of African Americans and in over 5% of West African populations. Occurring predominantly in males, V122I FAC is a late onset (age > 60 years) syndrome in which amyloid deposition is largely restricted to the heart and manifests as heart wall thickening with diastolic and systolic dysfunction, conduction defects, and arrhythmias, leading to congestive heart failure and death; neuropathy is uncommon. While the rate of disease penetrance in carriers of the mutation remains undefined, it is estimated that up to 150,000 older male African Americans in the United States carry the V122I gene, and there could be approximately 40,000 V122I cases worldwide. Another cardiac predominant TTR mutation, T60A, manifests as a disease of the heart and the autonomic nerves with less than one quarter of patients suffering from sensorimotor neuropathy. The T60A mutation affects approximately 1% of the population in northwest Ireland, but can also be found in other countries including Japan. Median survival after diagnosis of FAC is approximately 2.5 years for V122I and 3.5 years for T60A.

In addition to FAC, another cause of TTR cardiac amyloidosis where neuropathy is uncommon is senile systemic amyloidosis (SSA), a non-hereditary form of ATTR occurring when WT TTR deposits as amyloid primarily in heart tissue resulting in cardiomyopathy. This disease is predominantly seen in men older than 70 years, and the clinical presentation is similar to that described for FAC. The prevalence of SSA is unknown, but autopsy studies suggest that up to 22%-25% of individuals > 80 years old have TTR amyloid deposits in the heart, although the degree of deposition is mild in the majority of cases. Median survival after diagnosis of SSA has been reported to be approximately 3.5 years.

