### **3.5. Exploratory Clinical Efficacy Assessments**

Clinical efficacy will be explored through mortality, hospitalization, and 6-MWT. Additional clinical assessments will be performed including echocardiogram, CMR, 99mTc imaging, circulating cardiac biomarkers (including NT-proBNP, troponins I and T), amyloid quantitation in fat pad aspirates, eGFR, mBMI, KCCQ, new onset or recurrence of atrial fibrillation, pacemaker placement, change in diuretic medication regimen, blood pressure, NYHA classification, and patient-reported QoL assessed by EQ-5D. Evaluations of clinical efficacy will be performed as part of Screening and approximately every 24 through 48 weeks during the treatment period.

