#### **8.2.9. Missing Data**

For continuous and categorical variables, data will be analyzed as reported, unless otherwise specified. No imputation will be performed unless clearly identified.

For time-to-event variables, such as overall survival, subjects missing death will be right-censored.

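### Cardiovascular mortality is to be shown as a Kaplan-Meier curve, which can overstate the cumulative incidence of cardiovascular death and never understates it in the same data (low priority)

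*Protocol*

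**What the plan says.** Section 8.2.4 of the protocol states: "All-cause mortality and cardiovascular mortality will be summarized using Kaplan-Meier curves". The Synopsis, under Clinical Efficacy Assessments, lists cardiovascular-related and all-cause mortality as separate items, so the protocol itself allows for deaths that are not cardiovascular. Sections 2.2 and 3.5 refer only to mortality in general; Section 3.5 reads "Clinical efficacy will be explored through mortality, hospitalization, and 6-MWT".

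Section 8.2.9 gives the censoring rule: "For time-to-event variables, such as overall survival, subjects missing death will be right-censored". The protocol names no competing-risk method.

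On context, Section 8.1 says "Approximately 25 patients who completed Study ALN-TTRSC-002 will be enrolled in this extension study" and Section 8.2 says "Statistical analyses will be primarily descriptive in nature". There is no control arm.

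**The concern.** Kaplan-Meier is the right summary for all-cause death. A Kaplan-Meier curve for cardiovascular death alone has to remove patients who die of another cause, and it does so by censoring them. Read as a risk, the curve then assumes that a removed patient goes on facing the same cardiovascular hazard as those still under observation. A patient who has died does not.

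A figure headed cardiovascular mortality will be read as the proportion of patients who died of a cardiovascular cause by a given day. One minus Kaplan-Meier is not that proportion, even when nobody is lost to follow-up, and a reader who takes it as such will read it too high. In a descriptive study the displayed curve is the result, so it should estimate what its label suggests.

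**Working it through.** The protocol states no figure for this curve, so there is nothing to reproduce. The check has three parts.

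**1. Direction.** Take a time with *d* cardiovascular deaths among *n* patients at risk.

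- Aalen-Johansen cumulative incidence rises by S_all(t−) × d/n, where S_all is Kaplan-Meier survival from any death.
- One minus Kaplan-Meier, with other deaths censored, rises by S_cv(t−) × d/n, where S_cv drops only at cardiovascular deaths.

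S_all takes every drop that S_cv takes, plus the drops at non-cardiovascular deaths, so S_cv ≥ S_all at all times. Hence 1−KM is never below the cumulative incidence. It is strictly above once a cardiovascular death follows a non-cardiovascular one, and equal otherwise.

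**2. Worked counts: 25 patients, complete follow-up.**

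- *16 deaths, 3 of them non-cardiovascular.* The share dying of a cardiovascular cause is 13/25 = 52.0%, and Aalen-Johansen gives this in every order of deaths. If the three other deaths come last, 1−KM is also 13/25 = 52.0%. If they come first, 22 patients remain at risk and 1−KM = 13/22 = 59.1%. The mean over all 560 orderings is 56.4%.
- *13 deaths, 1 of them non-cardiovascular.* The share is 12/25 = 48.0%. 1−KM runs from 48.0% (other death last) to 12/24 = 50.0% (other death first), with mean 49.2%.

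The planned summary therefore depends on the order of deaths even with nobody lost.

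**3. Expected size at Day 1344.** Inputs from the protocol:

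- End of Study visit at Day 1344 (Table 2): t = 1344/365.25 = 3.68 years.
- Median survival, from Section 1.1.2: "Median survival after diagnosis of FAC is approximately 2.5 years for V122I and 3.5 years for T60A" and "Median survival after diagnosis of SSA has been reported to be approximately 3.5 years".

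Assumptions: hazards are constant; these medians, which run from diagnosis, are applied from first dose; and *q*, the share of deaths that are non-cardiovascular, is varied because the protocol does not give it.

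Formulas: H = (ln 2 / median) × t; cumulative incidence = (1 − q)(1 − e^(−H)); 1−KM = 1 − e^(−(1−q)H).

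For a median of 3.5 years, H = 0.729 and all-cause mortality is 51.7%. For 2.5 years, H = 1.020 and all-cause mortality is 63.9%.

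| Median (years) | q | Cumulative incidence | 1−KM | Excess (points) |
|---|---|---|---|---|
| 3.5 | 5% | 49.2% | 50.0% | 0.8 |
| 3.5 | 10% | 46.6% | 48.1% | 1.5 |
| 3.5 | 20% | 41.4% | 44.2% | 2.8 |
| 3.5 | 40% | 31.0% | 35.4% | 4.4 |
| 2.5 | 5% | 60.8% | 62.1% | 1.3 |
| 2.5 | 10% | 57.6% | 60.1% | 2.5 |
| 2.5 | 20% | 51.2% | 55.8% | 4.6 |
| 2.5 | 40% | 38.4% | 45.8% | 7.4 |

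The excess shrinks with longer survival. For q from 5 to 40% it is 0.3 to 1.7 points at a 6-year median and 0.1 to 0.7 points at a 10-year median.

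In simulated data sets of 25 patients with complete follow-up (20,000 per setting), 1−KM was never below Aalen-Johansen. At the protocol's medians it was strictly above in 71 to 99.8% of data sets for q of 10 to 40%, and in 45 to 54% for q of 5%.

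For scale, the 95% half-width is 1.96 × √(CIF(1 − CIF)/25). At a cumulative incidence of 41.4% this is 1.96 × √(0.414 × 0.586/25) = 19.3 points; over the table's range it is about 18 to 20. One patient is 1/25 = 4 points.

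**The case against.** The strongest reply is that Section 8.2.4 promises only a curve. It does not call 1−KM a risk or fix an estimate at Day 1344. A Kaplan-Meier curve that censors other deaths is a recognised display of the cause-specific hazard, and in that reading the assumption about removed patients is not needed. This is fair as theory, but the protocol nowhere states that reading, and a mortality summary set beside the all-cause curve will be taken as risk.

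A second reply is that censoring conventions, or a supplementary cumulative incidence curve, may be in the statistical analysis plan, which Section 8.2 says will be finalised before database lock. That stands as far as the silence of Section 8.2.9 goes, and the point does not rest on that silence. It rests on the method that Section 8.2.4 names.

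Third, the effect may be very small. Section 1.1.2 describes a disease centred on the heart, which suggests, without proving, that most deaths will be cardiac. At a 5% non-cardiovascular share the excess is a third of a patient or less (1.3/4 = 0.33), and the 40% rows look extreme. No stated objective names cardiovascular mortality separately, and the all-cause curve, which is correct, serves the mortality objective in Section 2.2. With so few deaths, a listing by cause would carry much of the same information. All of this stands and is why the priority is low. It does not make the named estimator the better one.

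**Conclusion.** The concern holds, at low priority. The direction of the discrepancy is algebraic and needs only the usual reading that non-cardiovascular deaths are censored in the cardiovascular curve. Its size rests on the constant hazards, the use of medians from diagnosis and the unknown non-cardiovascular share set out above, and under the protocol's medians it is well inside sampling error.

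The inequality compares two estimates from the same data. It does not mean that the reported figure must exceed the true population value: for shares of 10 to 40%, the simulated 1−KM fell below the population cumulative incidence in 25 to 45% of data sets through sampling error alone, and non-random dropout could have the same effect. No test or sample size depends on this curve.

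**What to change.** Keep Kaplan-Meier for all-cause mortality. Summarise cardiovascular mortality by the Aalen-Johansen cumulative incidence function, with non-cardiovascular death as a competing event.

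In Section 8.2.4 this is one sentence and a standard routine. No new data are needed, because the planned cardiovascular summary already requires cause of death. Section 1.3 shows patients already on treatment, and Section 9.2.3 sends amendments to the ethics committee and the regulatory authority, so an amendment for this alone is hard to justify. The cheaper route is to specify the cumulative incidence curve in the statistical analysis plan before database lock and correct Section 8.2.4 if the protocol is amended for another reason.

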#### **8.2.5. Healthcare Utilization Assessments**

The observed values and changes from baseline in a health care utilization questionnaire will be summarized.

